6. STUDY PROCEDURES

Provide detailed description of all study visits, procedures, and data collections, including:

- **Description of each study visit and procedures at each visit (include a schedule/table of study procedures)**

Initial enrollment (~30 to 60 minutes total):

After the consent, our trained study clinician will administer the intervention to the participant in-person, on the phone, or over zoom depending on participant preference. After the intervention is completed, the RA will obtain post-enrollment questionnaires and also schedule dates/times for the follow-up appointments. With participants' permission, the study clinician will document the clinically important findings elicited from the participant (e.g., preferences for end-of-life care goals) in Epic's ACP module and also send an email regarding the findings to patient's outpatient clinicians within Mass General Brigham health system via secure email. The study team will also provide the post-enrollment patient handout (see attachment) to the participants. All participants in the intervention arm will receive the same intervention and follow-up procedures.

Follow-up appointments (~30 to 45 minutes each):

During the scheduled follow-up appointments on the phone/zoom, our RA will administer surveys to assess for the outcomes. In addition, if the participants report that they have not had conversations with their outpatient clinicians about ACP, our study clinician will conduct brief coaching to overcome the obstacles participants might be facing in this process and also document clinically relevant information in Epic to notify to the outpatient clinician.

Table 3 Study visits		
Study visit	Intervention	Outcome assessment
Initial enrollment	ED GOAL	Post-enrollment survey

1-month follow-up	ACP navigation coaching (as needed)	Follow-up patient-reported outcomes surveys
3-month follow-up	ACP navigation coaching (as needed)	Follow-up patient-reported outcomes surveys
6-month follow-up	ACP navigation coaching (as needed)	Follow-up patient-reported outcomes surveys

- **Description of study drugs, devices, or other interventions/exposures administered, including:**

- **Dose, method of administration, schedule of administration, dose modifications**

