Our intervention is followed by scheduled, follow-up visits at one, three, and six months afterwards. The follow-up visits will be performed to assess the outcomes as well as to serve as the ACP care navigation/coaching by our study clinician.

Study clinician training:

We will train the study clinicians to administer these tools by 3-hour didactic on the concepts of delirium, cognitive impairment, and dementia, as well as bedside practice administration with the PI until competency is demonstrated (PI will self-record the responses next to the study clinician administering the instrument and compare the results. We will repeat this process with new patient volunteers until there is no discrepancy). In the case of equivocal findings on these assessments administered by study clinician, the PI backup will be available.

Intervention fidelity:

To ensure that all study clinicians deliver our intervention consistently, we will check the intervention fidelity. The percent adherence to the intervention fidelity checklist will be measured for every participant encounter (see attached fidelity checklist). High fidelity will be defined as mean adherence of >70% to the components on the fidelity checklist, which is consistent with expert consensus for behavioral intervention studies.²⁸

- **Justification and safety information if FDA approved drugs will be administered for non-FDA approved indications (“off-label”): How are doses, routes of administration, or participant populations different from FDA approved indicated use?**

Not applicable.

- **Description of specific data variables to be collected, including data collection methods, assessments, data collection sheets, and/or schedule of assessments (A schedule/table of study assessments is preferred)**

Measures	Descriptions	Timing
ACP engagement survey for patients (primary outcome)	Used for patients , this validated instrument will measure the self-reported processes for ACP (knowledge, contemplation, self-efficacy, and readiness), and ACP behavior. ²⁹	Baseline & at 1, 3, and 6 months
ACP engagement survey for caregivers (primary outcome)	Used for surrogate decision-makers , this ACP engagement survey is validated to measure the same ACP processes and behaviors. ³⁰	Baseline & at 1, 3, and 6 months

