Verbal consent will be obtained from the patient / caregiver participants. After learning about the general background of the study and reading the study information sheet (electronic or hardcopy), the potential participants will be able to decline to participate. Further, if the participant expressed anxiety or distress from the intervention (determined by the treating clinician), he/she is offered to discontinue the study and the PI will be responsible to care for the participant's emotional needs. The PI will also contact the patient's primary outpatient clinician to ensure adequate follow up of the patient after leaving the ED.

- **When appropriate, researchers use procedures already being performed on subjects for diagnostic or treatment purposes**

Not applicable.

8. Benefits

Provide detailed description of potential benefits of study participation, including:

- **Either describe potential benefits to participating individuals or clearly state that there is no direct benefit to individuals**

No definitive benefit has been demonstrated. However, our prior pre/post-intervention studies indicated that the intervention may lead to increased ACP engagement in patients with serious illness (see **Previous Studies** section above).

- **If multiple subject populations are to be enrolled, describe any differences between groups with regard to potential benefit (e.g. potential for benefit to an affected subject population versus no potential benefit for healthy controls, etc.)**

Based on the demographic data that we have thusfar, we do not anticipate differences between groups with regard to the potential benefit.

- **Potential benefits to society (e.g., increased understanding of disease process, etc.)**

For our patients, we hope that our intervention will lead patients to have more ACP conversations with their outpatient clinicians and loved ones. ACP conversations can lead to well-informed shared decision making and improved quality of life at the end of life.¹ For the society, ACP conversations are associated with lower rates of in-hospital death, less aggressive medical care at the end of life, earlier hospice referrals, increased peacefulness, and a 56% greater likelihood to have end-of-life wishes known and followed.¹⁻⁸ Furthermore, patients with documented ACP conversations experience a 36% reduction in the cost of end-of-life care, with an average cost savings of \$1,041 per patient in the last week of life.⁹

9. Statistical Analysis

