Describe plans for statistical analysis, including:

- **Statistical methods/data analysis plan**

Aim 1 quantitative data analysis:

We will conduct an intention-to-treat analysis. Since the primary outcome is mean change in self-reported ACP engagement, we do not expect differences among patients who are admitted vs. discharged. For our secondary outcome, we suspect that there is a propensity of more ACP documentation in patients who are hospitalized and missingness in patients who are primarily cared for at outside institutions. We will plan to use regression in subgroup analysis for ACP documentation to account for hospitalization status. In addition, we will perform sensitivity analyses to account for clustering by individual outpatient clinicians, palliative care consultations, and cognitive impairment status. We will also perform sensitivity analyses for survey respondents (e.g., patients vs. caregivers). We will compare patient demographics by study arm to assess randomization using bivariable analyses (t-test for continuous variables and chi-square for categorical variables). The mean changes in ACP engagement (primary outcome) at one month will be compared by study arms to estimate effect sizes. Within arms, we will use a one-sample binomial exact test of proportions for categorical outcomes (e.g., EMR documentation), and Wilcoxon signed ranks test for ordinal outcomes (e.g., ACP Engagement Survey) at baseline, after the intervention at one month. A p-value of 0.05 will be the significance threshold. To address missing data, I will conduct a secondary analysis using linear mixed models at baseline and one month. For qualitative outcomes,

Aim 2 qualitative data analysis:

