We will conduct in-depth, semi-structured interviews with participants. We will explore the perceived benefits of the intervention as well as barriers to completing ACP conversations after leaving the ED. The interviews will be recorded and professionally transcribed. The transcripts will be analyzed to identify recurring themes that illustrate the qualitative benefits (e.g., how the intervention changed their lives) and barriers to completing ACP conversations (e.g., how attempted ACP conversations were unsuccessful). Transcripts will be analyzed by two trained researchers to ensure interpretive integrity and consistency per standard comprehensive qualitative analysis methods. We will use framework analysis as the analytic approach,³³ which allows the flexibility of incorporating *a priori* considerations as well as more emergent themes in the data. The coding structure will be collaboratively and iteratively developed by the research team and include both prefigured and emergent codes.³⁴ We will use an ethnographic data management software program, NVivo 10 (QSR International). If there are disagreements, the mentors/advisors and we will review the quotes and themes to discuss their meaning and to achieve consensus. We will follow the consolidated criteria for reporting qualitative research.³⁵

- **Power analysis (e.g., sample size, evaluable subjects, etc.)**

For Aim 1 (quantitative data):

While this pilot RCT study is not powered to detect statistically significant differences in the ACP outcomes, we will compare 1-, 3-, 6-month ACP outcomes in the intervention arm to the control arm to estimate the preliminary effect sizes. Our prior study demonstrated a mean patient-reported ACP engagement increased from 3.8 to 4.3 on a 5-point scale, corresponding to a moderate effect size of 0.50.³⁶ A conservative estimate of effect size is 0.25. We also expect that 10% of enrolled patients will die before completing all follow-ups. With a sample size of 60 patients per group, we would have 90% power to detect the difference using a 2-sided Fisher's exact test ($\alpha=0.05$). We plan to exclude patients who die before 6-month in the analysis.

For Aim 2 (qualitative data):

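### The rule for distress caused by ED GOAL offers leaving the study but states no way to stop the intervention and stay in the surveys: a small, one-arm route to losing the one-month self-report

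*Combined protocol and SAP*

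**What the plan says.** The rule stands in Section 7, under the steps taken to decrease risks. Its trigger is "if the participant expressed anxiety or distress from the intervention (determined by the treating clinician"). The response is that "he/she is offered to discontinue the study and the PI will be responsible" for emotional care. The next sentence adds that the PI contacts the patient's main outpatient clinician.

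Section 6 bears on how the one-month data are collected:

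- **First contact.** Under Initial enrollment: "After the intervention is completed, the RA will obtain post-enrollment questionnaires and also schedule dates/times for the follow-up appointments". The measures table also lists a baseline for the ACP engagement surveys.
- **Follow-up contacts.** One sentence gives them two purposes: "The follow-up visits will be performed to assess the outcomes as well as to serve as the ACP care navigation/coaching by our study clinician". The more detailed text under Follow-up appointments divides the work: "During the scheduled follow-up appointments on the phone/zoom, our RA will administer surveys to assess for the outcomes". The study clinician coaches only when a participant reports no ACP conversation with outpatient clinicians, and Table 3 marks coaching as needed at 1, 3 and 6 months.

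The control arm is usual care (Section 5, randomization). Section 9 takes mean change in self-reported ACP engagement at one month as the primary outcome and compares it between arms to obtain effect sizes. On analysis it says "We will conduct an intention-to-treat analysis" and "To address missing data, I will conduct a secondary analysis using linear mixed models at baseline and one month".

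**The concern.** The rule answers a reaction to the intervention with a choice about the whole study. A participant may want no more of ED GOAL yet be willing to answer a survey a month later. The protocol does not tell staff to offer that.

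Up to the one-month survey the exit is confined to one arm. Controls have no session to be distressed by, and coaching first occurs at the one-month visit itself. Those who take the exit may also be people in whom the session worked poorly, so the loss may depend on the outcome.

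The planned analysis cannot fully repair this. Intention-to-treat keeps people in their assigned arm but does not supply scores that were never collected. The mixed model is secondary and valid only if the loss is at random given what was observed. Since the enrollment text puts the questionnaires and the booking of follow-up after the session, someone who stops midway may also lack a baseline score and an appointment.

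What is at stake is the effect-size estimate that this pilot is meant to hand to a larger trial.

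**Working it through.** **The plan's own figure.** There is none on this point. Section 9 expects 10% of patients to die before completing follow-up but gives no rate for distress or withdrawal. What follows is a range under assumptions.

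**Inputs**
- From the plan: 60 per arm (Aim 1); prior effect 0.50; "A conservative estimate of effect size is 0.25" (Section 9). I read both effects as standardized mean differences because they follow a sentence about mean engagement scores. The plan then names Fisher's exact test, so this reading is itself an assumption.
- Assumed: k = 1, 3 or 6 of the 60 ED GOAL participants leave by this route, so p = k/60; d = how much smaller the leavers' one-month change would have been than the stayers', in SD.

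**Shift in the completer comparison.** The full-arm mean is (1 − p) × stayers + p × leavers. Completers show only the stayers' mean, so the shift is p × d. The standard error with 60 per arm is √(2/60) = 0.183 SD. Each cell gives the shift in SD, then the shift divided by 0.183.

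| d | 1 of 60 | 3 of 60 | 6 of 60 |
|---|---|---|---|
| 0.25 | 0.0042 (0.02) | 0.0125 (0.07) | 0.025 (0.14) |
| 0.50 | 0.0083 (0.05) | 0.025 (0.14) | 0.050 (0.27) |
| 1.00 | 0.0167 (0.09) | 0.050 (0.27) | 0.100 (0.55) |

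At d = 0.25 a leaver changes like a control under the plan's conservative effect. The first row is then 1.7%, 5% and 10% of 0.25. d = 1 is twice the prior effect and is shown as an extreme.

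**What the fix could recover.** p × d is the ceiling. If half of the leavers accept the surveys, about half is recovered: at d = 0.25, 0.002 SD (1 of 60) to 0.013 SD (6 of 60).

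**Precision.** With k lost, SE = √(1/60 + 1/(60 − k)) and two-sided power is Φ(effect/SE − 1.96). For k = 6, SE = 0.188. Power at an effect of 0.50 falls from 78.2% to 76.0%, and at 0.25 from 27.7% to 26.5%. Loss of precision is not the issue.

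**Direction (illustrative only).** A simulation used 8,000 runs, 60 per arm, 6 leavers, an assumed baseline to one-month correlation of 0.5, and baseline observed for all. Here d is the gap given baseline, not the gap in change as in the table. When leavers start 0.96 SD lower, regression to the mean raises their expected change by (1 − 0.5) × 0.96 = 0.48, so the gap in change is d − 0.48. Multiplying by p = 0.1 gives −0.023, +0.002 and +0.052 SD for d = 0.25, 0.5 and 1; the simulated completer errors were −0.022, +0.002 and +0.052. The sign can thus go either way. A two-time-point likelihood model stayed off by 0.026, 0.050 and 0.100, close to p × d. That result follows from building in loss that is not at random, so it shows what the mixed model cannot remove, not how likely such loss is.

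**The case against.** The best defense is that this text protects participants and is not a retention rule. It answers a template prompt about avoiding unnecessary risk, it makes an offer that can be refused, and full exit is a defensible choice in a minimal-risk pilot. Much of this stands, and it limits the point in several ways.

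- **Numbers should be low.** The treating clinician must judge the distress, and for people enrolled by phone or Zoom after discharge no such clinician is described as present. Table 1 excludes people in acute distress, those judged not appropriate, and those unwilling to schedule follow-up.
- **The wording may mean less than it says.** Discontinuing could mean ending the session. If so, the remedy is to say that.
- **The information sheet was not available for this review.** It may set terms for partial withdrawal.
- **Some outcomes are untouched.** EMR documentation, utilization and vital status need no contact with the participant.

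A reader might also infer more than the documents support:

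- *That distress is met with nothing but an exit.* The same text provides PI care and contact with the outpatient clinician.
- *That staying in follow-up means accepting coaching.* The sentence giving the visits a double purpose suggests this, but the detailed text has the RA give the surveys and makes coaching conditional. Survey-only contact already fits the plan.
- *That anyone who stops the session is withdrawn.* No sentence says so.
- *That the template item on early end of participation, answered as not applicable, rules out continued follow-up.* That item concerns participants receiving therapy and sets no follow-up rule.

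What remains after these allowances is that the protocol states one participation option where two are needed.

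**Conclusion.** The point holds as a minor one. As written, the rule opens a route to missing one-month self-report that exists only in the ED GOAL arm before that survey, and the planned analysis cannot be relied on to undo the loss. At the assumed d = 0.25 the shift is 0.004 to 0.025 SD for 1 to 6 of 60 leaving, at most about one seventh of a standard error. Larger shifts need both many leavers and a large gap; the extreme case of 0.10 SD takes 6 leavers and d = 1.

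It would be tempting to say that the effect of ED GOAL will be overstated. The documents do not support that: neither the rate nor the direction is known. The conclusion rests on reading the phrase as leaving the study, on the information sheet not already providing a middle option, and on at least some leavers being willing to answer surveys.

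**What to change.** In Section 7, make stopping the session or later coaching a separate offer from withdrawing, with full exit still available. State that those who stop:

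- remain in their randomized arm;
- are offered the 1-, 3- and 6-month RA surveys without coaching, which they may decline;
- have chart review continued where the information sheet permits and permission has not been withdrawn.

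Record the reason and date of each stop or withdrawal, and report counts by arm. The decision to stop stays with the participant and the clinicians. If the existing phrase was meant as ending the session only, say so in the same place.

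The cost is a sentence or two and one reason-and-date field. The real downside is a few optional contacts about end-of-life planning with seriously ill people who found the topic distressing; dropping the coaching and keeping the right to decline limit that burden.

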- **Specify objectives and hypotheses to be tested in the research project**

Aim 1: Pilot test, in a randomized controlled design (N=120, 60 in each group), the effect of *ED GOAL* administered by trained nurses on patient and caregiver ACP engagement one month after leaving the ED.

Hypotheses: ACP engagement (a composite outcome combining patient-reported and EMR outcomes) will significantly increase in those who received *ED GOAL* compared to usual care.

Aim 2: Identify the patient-perceived benefits and obstacles of ACP conversations after *ED GOAL* using semi-structured interviews (N~30).

[figure not shown]
Rationale: Most patients who underwent our intervention in prior studies expressed their gratitude and reported how helpful the intervention was in their lives. Yet, these perceived benefits (“opened my eyes about what I need to focus in my life”) may be difficult to capture using validated, quantitative instruments. Furthermore, we will also elicit patient-perceived barriers to completing the ACP conversations.

3. General Description of Study Design

- **Explain the basic study design, e.g., parallel group, randomized controlled trial, open-label single arm study, cross over, adaptive, etc.**

This is a two-armed, parallel-design, pre-/post-intervention assessment study. We will conduct a randomized controlled trial for *ED GOAL* on a cohort of 120 older adults with serious illness to collect patient-centered outcomes and determine preliminary efficacy on increasing ACP engagement (self-reported and/or in the electronic medical record) one month after leaving the ED. We will also conduct qualitative interviews with participants of *ED GOAL*.

- **Provide study schema as applicable (a schema is required for greater than minimal risk studies, and optional for minimal risk studies)**

4. Subject Selection

Describe sources of subjects and procedures for subject selection, including the following:

- **Inclusion/Exclusion Criteria**

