EMR documentation (primary outcome)	Review EMR to see if new documentation of ACP conversation, change in code status, or advance directive forms documented by physicians or mid-level providers exist.	Baseline & at 1, 6, and 12 months
Self-reported ACP conversation survey (primary outcome)	Quantitative and qualitative questionnaires to assess the self-reported completion of ACP conversations with outpatient clinicians and families as well as barriers/facilitators of this process.	At 1, 3, and 6 months

Heard and understood survey (secondary outcome)	A validated instrument for seriously ill patients to report how well they feel heard and understood about their wishes for end-of-life care. ³¹	Baseline & 1, 3, and 6 months
Quality of communication survey (secondary outcome)	A validated instrument to measure the quality of communication about end-of-life care. ³²	Baseline & at 1, 3, and 6 months
Healthcare utilization (secondary outcomes)	Review EMR to see # of urgent care visits, ED visits, hospitalizations, hospice visits, and outpatient visits.	At 6 and 12 months before and 1, 6, 12 months after enrollment
Mortality	Review EMR to determine patient's vital status.	At 1, 3, and 6 months
Qualitative benefits and obstacles of ACP conversations after ED GOAL (secondary outcome)	Semi-structured interviews to assess the benefits of ED GOAL and obstacles participants faced in completing more ACP conversations with their outpatient clinicians and loved ones after ED GOAL (see interview guide).	At 1, 3, and/or 6 months

- **Description of planned genetic research as applicable (e.g., specific description of whole genome sequencing, creation of immortalized cell lines or induced pluripotent stems cells, and sharing of genetic material with collaborators and central repositories as applicable, etc.)**
Not applicable.
- **Description of plans for return of research results as applicable (e.g., specific description of, rationale for, and process by which research results will be returned, including to whom, by whom, and when, etc.). Include plans for managing incidental findings as applicable.**
Not applicable.
- **Definition of primary and secondary outcomes/endpoints. Note that outcome measures should be quantifiable and measurable.**
Please see **Table 4** above.
- **Definition of study termination criteria, e.g., objective criteria for clinical worsening, lack of improvement, and/or unacceptable adverse events**

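### The primary outcome is defined in three conflicting ways, and the 90% Fisher power figure does not apply to the one Section 9 analyses

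*Combined protocol and SAP*

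**What the plan says.** The document describes the primary outcome in three ways.

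- **Composite.** The Aim 1 hypothesis in Section 2 reads "ACP engagement (a composite outcome combining patient-reported and EMR outcomes) will significantly increase". Section 3 speaks of "increasing ACP engagement (self-reported and/or in the electronic medical record) one month after leaving the ED". Neither says how a survey score and a record finding are combined.
- **Four measures.** The measures table in Section 6 has the entries "ACP engagement survey for patients (primary outcome", "ACP engagement survey for caregivers (primary outcome", "EMR documentation (primary outcome" and "Self-reported ACP conversation survey (primary outcome", each bearing the primary label. The endpoint-definition item in Section 6 only points back to this table.
- **One mean change.** The Aim 1 analysis in Section 9 says "Since the primary outcome is mean change in self-reported ACP engagement". It repeats the primary label for the one-month mean changes compared by arm. On documentation it says "For our secondary outcome, we suspect that there is a propensity of more ACP documentation in patients who are hospitalized".

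The Aim 1 power paragraph in Section 9 first says the pilot lacks power to detect significant differences in the ACP outcomes. It then cites a rise from 3.8 to 4.3 on a 5-point scale as an effect size of 0.50, takes 0.25 as a conservative value, expects 10% deaths, and claims 90% power with 60 per group by a two-sided Fisher's exact test at 0.05. Patients who die before six months are to be excluded.

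**The concern.** EMR documentation is primary in Section 6 and secondary in Section 9. The four labelled measures may be meant as components of the Aim 1 composite, but nothing says so, and Section 9 then leaves two of them out (EMR documentation and the self-reported conversation survey). Depending on the section followed, the primary result is a difference in mean scores or a yes/no rate, with documentation in it or not. Nothing stops that choice being made after the data are seen.

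The power statement has a separate fault. Fisher's exact test compares proportions and cannot analyse a mean change, yet its effect sizes come from a mean.

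No confirmatory error rate is at stake, because the trial is a pilot that estimates effect sizes. But Aim 1 predicts a significant increase, Section 9 sets a 0.05 threshold, and Section 1 says the findings will support a definitive multi-site trial. The effect size carried into that trial would depend on which endpoint was picked.

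**Working it through.** **Inputs from the documents.** 60 per arm; two-sided alpha 0.05; effect sizes 0.25 and 0.50; 10% deaths, so 60 × 0.9 = 54 per arm once they are excluded. Section 9 does not say which SD the 0.50 refers to. Section 1 reports the same 3.8-to-4.3 rise as self-efficacy, which is only one part of the engagement survey described in Section 6.

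**Assumptions.** The documents give no baseline-to-follow-up correlation r (0.3 to 0.7 used here) and no control-arm rate (mainly 5% to 50% used here).

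**1. The plan's 90%.** It cannot be reproduced. A Fisher calculation needs a rate in each arm, and none is stated.

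**2. Section 9 primary, unadjusted, effect in SDs of the change.** Power from the noncentral t with 2n − 2 degrees of freedom and noncentrality d × √(n/2).

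| n per arm | d | Noncentrality | Power |
|---|---|---|---|
| 60 | 0.25 | 0.25 × √30 = 1.37 | 27% |
| 60 | 0.50 | 0.50 × √30 = 2.74 | 78% |
| 54 | 0.25 | 0.25 × √27 = 1.30 | 25% |
| 54 | 0.50 | 0.50 × √27 = 2.60 | 73% |

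For 90% power this analysis needs d = 0.597 at 60 per arm, or 338 per arm at d = 0.25. The 95% CI half-width is t × √(2/n): 1.980 × √(2/60) = 0.36 SD with 60, and 0.38 SD with 54.

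**3. Same analysis, effect in SDs of the score.** SD of change = SD × √(2(1 − r)), which is 1.18, 1.00 and 0.77 score SDs at r = 0.3, 0.5 and 0.7.

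| n per arm | d | Power, r = 0.3 to 0.7 |
|---|---|---|
| 60 | 0.25 | 21–42% |
| 60 | 0.50 | 63–94% |
| 54 | 0.25 | 19–38% |
| 54 | 0.50 | 59–91% |

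**4. Baseline-adjusted, effect in SDs of the score.** Residual SD = SD × √(1 − r²), which is 0.95, 0.87 and 0.71.

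| n per arm | d | r = 0.3 | r = 0.5 | r = 0.7 |
|---|---|---|---|---|
| 60 | 0.25 | 30% | 35% | 48% |
| 60 | 0.50 | 81% | 88% | 97% |
| 54 | 0.25 | 27% | 32% | 44% |
| 54 | 0.50 | 77% | 84% | 95% |

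Half-widths with 60 per arm are 0.35, 0.31 and 0.26 score SDs. If the effect is in SDs of change instead, power with 60 at the same three correlations is 39%, 35% and 31% (d = 0.25) and 92%, 88% and 84% (d = 0.50).

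**5. A yes/no endpoint, reading 0.25 as a 25-point difference.** Exact power of the two-sided Fisher test:

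| Control rate | n = 60 | n = 54 |
|---|---|---|
| 5% | 95% | 92% |
| 10% | 89% | 85% |
| 15% | 83% | 79% |
| 30% | 75% | 68% |
| 50% | 76% | 72% |

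Within control rates of 5% to 50%, 90% is reached only at about 9% or lower with 60 per arm, or about 6% or lower with 54.

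**The case against.** The strongest reply has four parts.

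- **The composite and the four labels may fit together.** Section 3 uses an and/or wording, and Table 2 pairs survey with EMR by cognitive group, so patient and caregiver surveys are alternatives except in dyads. This narrows the conflict to the composite against Section 9. It does not remove it: and/or does not say how a mean score enters, the conversation survey is not in Table 2, and EMR documentation still has both labels.
- **It is a pilot with an express disclaimer about power.** That is true, and it limits the consequence. But a study meant to estimate an effect must say which effect, and the disclaimer contradicts the 90% in the same paragraph.
- **90% could be right for a binary endpoint.** This stands as a limit. Section 1 reports 26% and 40% documentation after the intervention. If those were intervention-arm rates and the difference 25 points, control would be 1% or 15%, and Fisher power 99% or 83% with 60 per arm (98% or 79% with 54). High rates can also reach it: 66% against 91% gives 90% with 60. The plan states no such endpoint or rates, so the figure is unsupported rather than shown wrong for every endpoint.
- **The correlations are not the plan's.** Correct, which is why ranges are shown. The unadjusted 27% and 78% need no correlation when the effect is in SDs of change.

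**Conclusion.** The concern holds and must be fixed. The primary outcome cannot be identified from the document, and the 90% does not describe the primary that Section 9 analyses. At the plan's conservative 0.25, two-sided between-arm power for that primary with 60 per arm runs from 21% to 48% over every version examined. At 0.50 it runs from 63% to 97% and depends on an SD and a correlation the plan does not state. These figures assume roughly normal scores, equal arms and, where used, correlations of 0.3 to 0.7. The textual conflict rests on no assumption.

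**What to change.** Choose one primary outcome at one month, state it identically in Sections 2, 3, 6 and 9, and relabel the other measures as secondary.

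**If it is the survey change:**
- Drop the composite from the Aim 1 hypothesis and report the between-arm difference with a 95% CI.
- State how patient and caregiver scores enter, since Table 2 assesses both in dyads.
- First reconcile Section 6 on timing. The measures table lists a baseline survey, while the enrollment text and Table 3 describe only questionnaires taken after enrollment, and the enrollment text places these after the intervention. Use change from baseline or baseline adjustment only if the baseline survey comes first; otherwise compare one-month scores.
- Replace the Fisher sentence with power or CI half-width for the model actually used, naming the SD. With 60 per arm, unadjusted change gives about 27% and 78%, half-width 0.36 SD of change. Baseline-adjusted analysis gives about 35% and 88%, half-width 0.31 score SD, at an assumed correlation of 0.5. Show the range over 0.3 to 0.7: 30–48%, 81–97% and 0.35–0.26.

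**If it is the composite:** write the and/or rule as a yes/no endpoint, state the assumed rate in each arm, and recompute Fisher power for 60 and 54 per arm.

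Either way, remove the 90% or reconcile it with the statement that the pilot is not powered.

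**Cost:** wording in four sections and a rewritten power paragraph. No new data are needed if the baseline survey precedes the intervention; if it does not, either its timing or the endpoint changes. The stated power becomes less favourable, and claims on the other labelled primaries become secondary.
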